Possible modifications to the device that we can anticipate occurring throughout the study are discussed in previous sections and briefly summarized here. The clinical actionability of all Mendelian disorders will continue to evolve over the foreseeable future. The development of the list of conditions that have been scored by the NC NEXUS Actionability team (Appendix 8) as described in Section 2, Defining Clinical Actionability is expected to continue throughout the study period and after, and therefore, periodic updates of the lists will occur. Slight changes or adjustments based on feedback from user testing may lead to minor changes in the Longitudinal Study Measures (Appendix 19) described in Section 5, Study Narrative. Among the major research activities of the NC NEXUS project will be the evaluation of new bioinformatics algorithms; in addition, we anticipate improvement in the evidence available to assess pathogenicity of variants (as defined in Section 2 Revised Results in the Follow-up Procedures, Section). Thus, by design there will be developmental changes in the protocol, accompanied by periodic reanalysis of the NGS data, with the possibility that the results of the analysis may change over time and some participants will be re-contacted for updated results. This situation will be clearly described in the informed consent.

The FDA will be provided with a 5-day notice of any updates or changes in the measures, lists that are implemented in the informatics algorithms, or types of revised results that are returned to patients.

Monitoring Plan/Procedures

The Sponsor-investigator (Principal Investigator) and key study personnel will meet on a quarterly basis to discuss aspects of the study, review unanticipated problems and adverse events, evaluate results, scrutinize data and anticipate problems relevant to subject safety. An independent Study Data Monitor and Medical Safety Monitor will be established prior to enrollment of participants. These individuals will meet with the Principal Investigator and other key study personnel as described below.

As our study involves a unique aspect of genomic sequencing in the pediatric population not typically considered under most “medical monitoring” plans,

including the option for some parents to receive results on variants in genes that are associated with carrier status and adult-onset conditions in their infant, we held a 2-day conference at the beginning of our project to solicit opinions about our proposed study protocol including return of results from an external group of consultants including experts in biomedical ethics, genetic counseling, newborn screening and clinical genetics. We received support for our plan as outlined above. These experts have agreed to continue to serve as external consultants throughout our study period and include [name], Director of the UNC Center for Bioethics, as well as others from outside our institution. They will be available as needed to review any ethical concerns or questions that arise.

STUDY DATA MONITOR

The data in this study will be reviewed on a regular basis by an independent data monitor. The role of the data monitor will be to review study documentation, regulatory files, and informed consent to ensure the quality and integrity of the data collected and adherence to good clinical practices. An important focus of the data monitoring will be to ensure appropriate informed consent has been obtained from the research participants.

MEDICAL SAFETY MONITORING

The Principal Investigator will oversee the safety of the study at her site. This safety monitoring will include careful assessment and appropriate reporting of adverse events as noted above. Medical monitoring will include a regular assessment of the number and type of adverse events as defined in section 8. Any safety concerns or unanticipated problems will be relayed to an independent medical safety monitor for immediate review. In addition, there will be a quarterly project meeting at which concerns can be raised for discussion by the entire project team. Such opportunities will allow us to monitor for the expected psychosocial impact of genetic testing as well as being alert to otherwise unexpected participant safety issues. The medical safety monitor will have expertise in pediatrics and research ethics. The role of the medical officer will be to advise the Principal Investigator and project team and make recommendations about continuing the study.

AUDITING AND INSPECTING

The investigator will permit study-related monitoring, audits, and inspections by the EC/IRB, the sponsor, government regulatory bodies, and University compliance and quality assurance groups of all study-related documents and study-related files. The investigator will help coordinate inspections of applicable study-related facilities.

Participation as an investigator in this study implies acceptance of potential inspection by government regulatory authorities and applicable University compliance and quality assurance offices.

ADDITIONAL RECORDS AND REPORTS

Reports from the study data monitor describing records reviewed, any concerns

noted, and recommendations made to correct deficiencies; as well as correspondence from the medical safety monitor following any necessary reviews will be provided to the IRB, FDA, and NHGRI/NICHD. Reporting will also include annual progress reports to NHGRI/NICHD.

DATA HANDLING AND RECORD KEEPING

Most of the data collected in the NC NEXUS study will be stored electronically as follows (and detailed below):

- A REDCap database managed by the North Carolina Translational and Clinical Sciences (NC TraCS) Institute will be used to store demographic information and baseline clinical data for each participant (parents and children) enrolled in the clinical study. This database is within the UNC Hospitals firewall and will serve as the database of record linking personally identifiable information with the unique study identifier. Entry and maintenance of the study records will be a shared responsibility of study investigators.
- Project-related tasks and laboratory data will be recorded in a custom workflow management system managed by RENCI that has access restricted to specific roles. No personally identifiable health information is included.
- Data from questionnaires will be stored on a secure drive at UNC with restricted access to only those personnel who are involved in data analysis.
- Data from the decision aid will be stored on a secure drive at RTI with restricted access to only those personnel who are involved in data analysis.
- Sequence data and called variants will be stored in the UNC Research Computing system. Raw sequence data will be stored for the duration of the study on tape backup through UNC Research Computing. A reduced representation of the participant's variant calls (currently in the form of a VCF file, although standard formats may change over time) and a file that comprises the clinically relevant variants to be reviewed and confirmed will be stored in a data repository managed by RENCI and will have access restricted to a subset of study personnel who are involved in data analysis.

Results that are confirmed in the MGL will be reported as clinical genetic test results and parents will be provided with a paper copy of the report for their personal records. These official reports will have participant names and medical record numbers and, if consent is given, will become part of the permanent medical record, subject to the protections afforded by the HIPAA regulations. Otherwise, subject names or other directly identifiable information will not appear on any reports, publications, or other disclosures of clinical study outcomes.

Record Maintenance and Retention

The investigator-sponsor will maintain records in accordance with Good Clinical Practice guidelines, to include:

- FDA correspondence related to the IDE application and Investigational Plan
 - IRB correspondence related to the clinical protocol, current and past versions of the IRB-approved clinical protocol and corresponding IRB-approved consent forms
- Signed Investigator's Agreements and Certifications of Financial Interests of Clinical Investigators
- Certificates of required training (e.g., human subject protections, Good Clinical Practice, etc.) for investigator-sponsor and listed sub-investigators
- Signed informed consent forms
- Copies of adverse event reports and annual or interim reports
- Monitoring visit reports
- Final clinical study report.

Confidentiality

Information about study subjects will be kept confidential and managed according to the requirements of the Health Insurance Portability and Accountability Act of 1996 (HIPAA). Those regulations require a signed subject authorization informing the subject of the following:

- What protected health information (PHI) will be collected from subjects in this study
- Who will have access to that information and why
- Who will use or disclose that information
- The rights of a research subject to revoke their authorization for use of their PHI.

In the event that a subject revokes authorization to collect or use PHI, the investigator, by regulation, retains the ability to use all information collected prior to the revocation of subject authorization. For subjects that have revoked authorization to collect or use PHI, attempts should be made to obtain permission to collect at least vital status (i.e. that the subject is alive) at the end of their scheduled study period.

All clinical information will be kept confidential, and will only be accessed by those directly involved in the research. The FDA may request and be granted access to the records. The digital file containing the linked participant names, UNC medical record numbers and unique study identifiers will be stored in a password-protected REDCap database managed by NC TraCS. Paper copies of consent forms and any personal health information will be stored in a locked filing cabinet in a locked office. All identifiers (name, date of birth, etc.) will be removed from the saliva samples before they are sent to the BSP or MGL and all samples used in this study will be labeled only with the participant's unique study identifier.

Genetic variant data: Each participant's genetic variant data will be stored using a unique participant ID number and stored for the duration of the study on tape

backup through UNC Research Computing. A file that comprises the clinically relevant variants to be reviewed and confirmed will be stored in a data repository managed by RENCI, which will have access restricted to a subset of study personnel. A reduced representation of the participant's variant calls will be stored with the unique participant ID number to allow for re-analysis.

Questionnaire Responses: Participants' responses to study questionnaires (research data) will be identified only by their unique participant ID number, whether collected in an online questionnaire format implemented in Qualtrics or in a paper-and-pencil questionnaire or interview by a trained staff member (e.g., for participants who cannot or prefer not to complete the online questionnaire). The questionnaires will not collect information that could be used to identify participants.

Decision Aid Usage Data: Data gathered through participant interaction with the electronic decision aid (e.g., app performance metrics, usage metrics, and participant inputs) will be associated with unique participant ID numbers. The decision aid will not collect information that could be used to identify participants. All usage data will be stored in a secure password protected database at RTI secured by industry standard firewalls and a stringent IT security policy framework. Data and query tools published via web interfaces will be encrypted.

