4. Non-canonical splice site variants include those that occur within 3-10 nucleotides of the intron-exon border.

5. UTR variants are annotated as being located in the 5’ untranslated or 3’ untranslated regions of the mRNA.

6. MAF data will be derived from frequency data from the 1000 Genomes Project and ExAC; the highest of the minor allele frequencies for a given variant from any ethnic group will be used to evaluate the MAF threshold criteria.

Integral to the efficient diagnostic assessment of an entire genome or exome will be the establishment of *a priori* panels of genes to be assessed under certain clinical situations. One of the major tasks of the clinical and molecular teams will be the development of such lists relevant to the categories of disorders that are present in the Diagnosed Cohort. Once established, these lists will be used to query patients’ variant data to identify all variants in genes of possible diagnostic significance in the context of their medical presentation. A molecular analyst will evaluate the prioritized variant list and provide a preliminary interpretation of the case to the molecular sign-out committee.

The committee will make a final pathogenicity determination and decide whether any variants exceed our threshold for reporting (Table 2). Because of the presence of a phenotype in the individual being sequenced, results considered to be clinically relevant would include the “known pathogenic,” “likely pathogenic,” and “variant of uncertain significance” as determined by the molecular sign-out committee.

Table 2: Categories of findings deemed reportable for an indication-based analysis

Result Category	Variant types	Zygosity	Phenotype ⁸	Inheritance
Positive-Definitive	KP ¹	Heterozygous	Concordant	Dominant ⁹
	KP	Homozygous or compound heterozygous ⁶	Concordant	Recessive ¹⁰
Positive-Probable	LP ²	Heterozygous	Concordant	Dominant
	KP	Potentially compound heterozygous ⁷	Concordant	Recessive

	LP	Homozygous or potentially compound heterozygous	Concordant	Recessive
--	----	---	------------	-----------

Uncertain-VUS	VUS ³	Heterozygous	Concordant	Dominant
	VUS,	Homozygous	Concordant	Recessive
	VUS plus KP/LP ⁴	Compound heterozygous or potentially compound heterozygous		
Uncertain-AR het	KP/LP ⁵	Heterozygous	Concordant	Recessive
Uncertain-Contributory	Any	Any	Partially matching	Any

1. KP = Known Pathogenic

2. LP = Likely Pathogenic

3. VUS = Variant of Uncertain Clinical Significance

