6 RISK ANALYSIS

The NC NEXUS research study was launched in response to a request from NIH (NICHD and NHGRI), to perform research studies to investigate next-generation sequencing studies in newborns. Although some ethical guidelines in the past have raised concerns about testing children for adult onset conditions, there are few, if any, studies looking at the outcomes of such testing. In order to satisfy the directives for obtaining additional information about this, we have proposed the NC NEXUS study to provide research data to begin to answer some of these questions.

Parents enrolled in the study will not be exposed to any significant physical or social harms. It is possible that they could experience psychological distress due to making decisions about having sequencing for their child, or deciding about whether to learn certain categories of information. One of the objectives of the NC NEXUS project is to study precisely these types of impacts that might accompany genomic sequencing of newborns. We estimate that 80% of the family units will be couples and 20% will be single parents, so with enrollment of 400 children in the study we expect to enroll 720 parents (400 female, 320 male). The majority will be between 20-40 years of age.

Children and newborns in the study will be exposed to theoretical physical, social, and psychological harms that have been discussed and debated in the medical literature. An additional source of risk relates to positive results (both true positive and false positive) and false negative results. Again, assessment of the magnitude of these potential risks is a major overarching goal of the NC NEXUS project. We estimate that the distribution of 400 children and newborns ages 0-5 enrolled in the study will be roughly 50% female and 50% male.

Anticipated Risks

Potential risks to which the subjects (parents and their children and newborns) will be exposed as a result of their participation in the clinical study can be divided between generic risks that are inherent to human subjects genetic research and risks that are specific and unique to the NC NEXUS project.

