- **Adverse effects associated with the investigational device due to medical interventions undertaken as a result of positive findings:**

1. There is a reasonable possibility that erroneous (non-standard of care) medical actions may have occurred as a consequence of positive findings.
2. There is a reasonable possibility that serious injury, hospitalization, or death may have occurred as a complication of standard of care medical follow-up of positive findings.

- ***Psychosocial complications of newly identified diagnoses:***

Positive findings from the NC NEXUS study may lead to low-level parental anxiety and/or distress. This is an expected reaction to a medical diagnosis and should be short-lived and relatively minor. Therefore, we will *not* consider the existence of mild or time-limited psychological complications as an adverse event. However, there may be rare instances in which study members deem the level of psychological distress to require referral to a specialist or other intervention. Therefore, we will monitor for any such adverse events, defined as:

Adverse psychosocial effects associated with the investigational device due to revelation of positive findings: There is a reasonable possibility that serious psychosocial harms may have occurred as a consequence of reporting positive genomic findings to the parents.

- ***False negative results:***

The NC NEXUS study is evaluating a screening test using a technology that is certain to have imperfect sensitivity for most genetic conditions. Therefore, there is a chance that some individuals in the study will develop a genetic condition that was not detected by the sequencing test (false negative results). This is a predictable event, and thus will *not* be considered an adverse effect, since these individuals would have the same outcome as if they had not enrolled in the study. With longitudinal follow-up over the course of the study it is possible that we will identify a small number of false negative results, but based on the sample size this is an extremely unlikely occurrence. Furthermore, all participants will already be receiving standard of care newborn screening and pediatric care and thus will not be relying on NC NEXUS for the detection of conditions that are currently deemed to be part of the recommended uniform screening panel.

- ***False positive results:***

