NGS technology (like any test) is known to have technical false positives, essentially variant calls that are due to errors in mapping, other variant calling artifacts, or inherent limitations in the current state of knowledge about the human genome (eg. unmapped pseudogenes). All results will be confirmed by Sanger sequencing in the CLIA-certified MGL, so it is very unlikely that any technical false positives will be inadvertently returned to participants. On the other hand, the process of variant analysis and interpretation is part of the practice of medicine and is subject to variability between laboratories. A board-certified molecular geneticist or pathologist will review and sign-out all results that are deemed returnable in the NC NEXUS study in order to ensure the highest threshold of quality. However, there is a possibility that some of the positive results could be reinterpreted in the future (and thus become false positive results). In this case, it is possible that actions may be taken due to the finding, which are later determined to have been unnecessary. Therefore, we will monitor for such adverse events, defined as:

Unnecessary medical care associated with the investigational device

due to false positive findings: There is a reasonable possibility that medical actions taken by the patient's physician were related to a genetic finding that was later deemed to be a false positive result.

- ***Other unexpected adverse effects:***

The NC NEXUS study may also involve risk for unexpected adverse effects, which we define as any incident, experience, or outcome that meets all of the following criteria:

- Unexpected in nature, severity, or frequency (i.e. not described in study-related documents such as the IRB-approved protocol or consent form, the investigators brochure, etc.)
- Related or possibly related to participation in the research (i.e. possibly related means there is a reasonable possibility that the incident experience, or outcome may have been caused by the procedures involved in the research)
- Suggests that the research places subjects or others at greater risk of harm (including physical, psychological, economic, or social harm).

Recording and Assessment of Adverse Effects

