 - the deviation was necessary to protect a subject from immediate harm
- **Breach of confidentiality**

Reporting Process

The reportable events noted above will be reported to the IRB using the form: “Reportable Event Form” or as a written report of the event (including a description of the event with information regarding its fulfillment of the above criteria, follow- up/resolution and need for revision to consent form and/or other study documentation).

Copies of each report and documentation of IRB notification and receipt will be kept in the Clinical Investigator’s study file.

Withdrawal of subjects from the study

The informed consent materials will clearly state that parents can withdraw from the study at any time, that this will not impact the child's medical care in any way. Parents who refuse to use the decision aids or fail to comply with the questionnaires will be considered withdrawn and their child’s sample will not undergo further sequencing or analysis. They will not participate in the randomization. Specimens from parents who desire to terminate participation will be destroyed and no further analysis of data in such individuals will be pursued.

Description of Investigational Device

On August 27, 2014, the FDA provided a response to a pre-submission inquiry and determined that the proposed NC NEXUS study would be required to submit an Investigational Device Exemption (IDE) due to the significant risk associated with the potential long-term consequences to both the parent(s) (i.e., psychological impact) and the child (i.e., denial of life and/or long-disability insurance and having medical records containing WES information of which he/she did not consent to) after learning of the WES finding. The FDA has determined that the decision aid that will be developed and the psychosocial research that will be conducted are also part of the “device” that is being evaluated. In that case, the “device” would be best described as:

“Informed parental decision-making aided by an electronic decision aid regarding their acceptance of next-generation sequencing newborn screening for their child; whole exome sequencing with targeted analysis and Sanger confirmation of positive findings; return of results through standard-of-care genetic counseling; and follow-up questionnaires regarding the psychosocial impact of the screening.”

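### The named adverse-event definitions cover only harm from positive findings, so serious harm from uncertain results, study decisions or insurance denial has no category and could be under-counted

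*Combined protocol and SAP*

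**What the plan says.** The definitions sit in the protocol under the headings numbered 7 and 8. Four kinds of event are named:

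- Non-standard care: "There is a reasonable possibility that erroneous (non-standard of care) medical actions may have occurred as a consequence of positive findings".
- Serious injury, hospitalization or death that "may have occurred as a complication of standard of care medical follow-up of positive findings".
- Psychosocial harm: "There is a reasonable possibility that serious psychosocial harms may have occurred as a consequence of reporting positive genomic findings to the parents".
- Unnecessary care after a finding that is later judged a false positive.

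False negatives are expressly not adverse effects, and the protocol gives its reason: the child is no worse off than if not enrolled.

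The catch-all, under Other unexpected adverse effects, has three criteria that must all hold. The first is "Unexpected in nature, severity, or frequency (i.e. not described in study-related documents such as the IRB-approved protocol or consent form". The third covers physical, psychological, economic and social harm and is not tied to any type of result.

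Recording and Assessment of Adverse Effects then asks for every observed or volunteered adverse effect with a reasonable possibility of being caused by the device, in either cohort and either arm. Description of Investigational Device makes the device the whole study, including consent, decision aid, return of results and questionnaires. It also reports why the FDA saw significant risk: psychological impact on parents and, for the child, "denial of life and/or long-disability insurance and having medical records containing WES information of which he/she did not consent to".

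Medical Safety Monitoring states: "Medical monitoring will include a regular assessment of the number and type of adverse events as defined in section 8".

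**The concern.** The protocol names several harms that need not follow from a positive finding. If an event must match a named definition to be counted, those harms depend on a catch-all whose first test works against anything already foreseen in the protocol or consent form. A low count of psychosocial or insurance events could then partly reflect how the events were defined. This matters because parental psychological impact and insurance denial are both among the reasons the FDA gave for requiring the IDE, and the Risk Analysis calls assessing the size of the potential risks to children a major goal of the project.

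**Working it through.** There is no plan figure to reproduce; the check sets the sections side by side. Arithmetic is used only for scale.

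**1. Is a returned uncertain result a positive finding?** Not in the protocol's vocabulary. On the indication-based analysis it says: "Because of the presence of a phenotype in the individual being sequenced, results considered to be clinically relevant would include the" pathogenic, likely pathogenic and uncertain classes. Table 2 then lists two Positive categories (Definitive, Probable) separately from three Uncertain ones (VUS, AR het, Contributory). Under Revised results, a variant downgraded from pathogenic to VUS may turn a positive result negative.

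**2. Each harm against each route**

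| Harm | Where the protocol raises it | Named definition | Catch-all | Recording rule with device description |
|---|---|---|---|---|
| Serious distress or non-standard care after an uncertain result | Such results are returned under Indication-based analysis, Table 2; possible distress from diagnostic results is in Risk Analysis | None | Distress: mainly if worse or more frequent than described | Can be read to include it |
| Distress or regret from the decisions | Risk Analysis: "It is possible that they could experience psychological distress due to making decisions about having sequencing for their child"; also Parental decision regret | None | Mainly if worse or more frequent than described | Can be read to include it |
| Insurance denial | Confidentiality; Financial (mitigation rated uncertain); FDA reasons | None | Mainly if worse or more frequent than described | Can be read to include it |

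**3. What the catch-all admits.** Its first criterion is met by an unexpected nature, severity or frequency. These harms mostly fail on nature because they are described. They can pass on the other two, since the protocol sets low benchmarks: insurance loss after a confidentiality breach is moderate and rare, distress needing referral is rare or infrequent, and added distress for Diagnosed Cohort parents is minimal. A serious event at the expected frequency may still fail.

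**4. What the recording rule adds.** It is broad, but it does not define an adverse effect more widely than the list before it, and it depends on events being observed or volunteered. The FDA list that follows (death, life threat, permanent impairment, intervention to prevent it) contains nothing psychosocial or economic.

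**5. Scale**

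Inputs: 400 children and 720 parents (Risk Analysis); 200 per cohort and 2:1 allocation (Study Design); fewer than 3% with previously unknown findings (Complications of medical management); more than 95% of Well-Child participants negative on NGS-NBS (Schedule of activities); 250 and 350 family units enrolled (Anticipated Number of Research Subjects).

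- Newly identified findings: 0.03 × 400 = 12, so fewer than 12 children. For parents, 0.03 × 720 = 21.6, so at most about 22. Positive indication-based results are extra, with no rate given. Carrier results must also be outside this figure, because the protocol expects them to be typical among those who request additional findings.
- Well-Child families with a negative screen: 0.95 × 200 = 190. At 720 / 400 = 1.8 parents per family, 190 × 1.8 = 342 of 360 parents. Some Decision families will later receive a positive carrier result.
- Well-Child controls, who get no additional results: 200 / 3 = 66.7 families; 66.7 × 0.95 = 63.3 with a negative screen; 63.3 × 1.8 = 114 parents.
- Families facing the additional-findings decision: 400 × 2/3 = 266.7, about 267.
- Families enrolled but not sequenced: 250 + 350 − 400 = 200, decliners and dropouts together. They receive no result, so no named definition can apply to them.

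**The case against.** The strongest reply is that the plan has other routes, and much of it stands.

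- The catch-all is not confined to positive findings and names psychological and economic harm.
- The recording rule, with the device defined as the whole study, can be read to take in decision-related harm and harm after any result. The FDA reporting text covers anticipated as well as unanticipated device effects.
- Medical Safety Monitoring says what monitoring will include, which is not a limit. It sends any safety concern to the independent monitor and uses quarterly meetings to watch for expected psychosocial impact. Its pointer to section 8 matches the heading above the definitions, so that is not an error.
- IRB reporting covers confidentiality breaches and certain complaints.
- Sequencing-related distress and decisional conflict are primary dependent variables. Distress is measured before and after results, regret is checked for rises of 0.5 SD or more, and flagged parents are discussed by the team. Time 3 and Time 4 questionnaires follow return of results whatever the result.
- Excluding false negatives is a reasoned choice.

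What the reply leaves open is the count itself. No text turns a flagged distress or regret case into an adverse event. Parents who decline sequencing leave after Time 2. The IRB route for adverse events again requires them to be unexpected. Nothing named covers insurance denial. The wide and narrow sections are not reconciled.

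**Conclusion.** The point holds as a gap in the named definitions and a conflict between sections. Counting strictly by the named definitions and the catch-all would under-record serious harm from uncertain results, from study decisions and from insurance denial. By how much cannot be said, since the documents give no event rates; 342 of 360 parents, like the other figures above, counts people outside a definition and does not estimate harm.

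This rests on two assumptions: that positive in the definitions carries its Table 2 meaning, and that whoever counts events follows the narrow list. If the recording rule governs instead, the gap shrinks to missing labels.

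A reader might infer three stronger things that the documents do not support:

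- These harms can never be adverse events, or the catch-all bars everything already described. It also admits unexpected severity or frequency.
- Insurance denial was the FDA's reason for the IDE. It is one of several, and the psychosocial definition partly covers another, parental psychological impact.
- The study could report no psychosocial harm at all. Distress and regret are measured as outcomes, including in families with negative results.

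**What to change.** 1. In the psychosocial definition, and in the two-item definition on non-standard medical actions and complications of follow-up, replace the reference to positive findings with *any returned result (positive, uncertain, negative or additional)*. In the psychosocial definition add *or any decision the study asks parents to make*. Make no blanket replacement: the false-positive definition would lose its meaning, and it should stay as it is. The false-negative exclusion also stays, so a missed diagnosis is still not an adverse effect in itself.
2. Add a named category for insurance denial or other discrimination attributed to a study result. Record it whenever observed or volunteered and ask about it at Time 4. State that later events may be missed, which the Risk Analysis already concedes for long-term harms; Time 4 comes only about three months after results.
3. Let the unexpectedness test govern expedited reporting only. State under Recording and Assessment of Adverse Effects that all device-related effects are recorded, expected or not.

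The cost is protocol wording, one questionnaire item, somewhat more events to record in REDCap and a less favourable-looking adverse-event count.
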